3.3 Secondary Outcomes (Aim 2)

Physical activity (PA), sedentary behaviors (SB), and sleep (min/day) will be measured in min/day.

3.4 Tertiary Outcomes (Aim 2)

Percentage over the 95th percentile in body mass index (BMI)

Psychological needs (Psychological Need Satisfaction in Exercise Scale), and autonomous motivation (Behavioural Regulation in Exercise Questionnaire-2).

4 Study Design

To address the research question, "**Is a technology-based intervention that promotes PA, SB, and sleep, feasible among Hispanic adolescents with obesity?**" a two-armed, pre-post design will be used to test the feasibility of the intervention compared to a wait-list control group. Limitations of previous studies include the absence of control groups.^{6,7} A wait-list control comparison is appropriate for studies in the pre-efficacy phase that aim to assess feasibility.⁸ Another limitation of previous studies is the use of self-reported measures to assess health behaviors.⁹⁻¹¹ We will rely solely on research grade accelerometers to objectively measure wake time and sleep behaviors at baseline (T0) and 12- weeks post-intervention. Following baseline assessments, youth will be randomized in a 1:1 ratio to the intervention or wait-list control using a computerized random number generator in SAS version 9.4 (SAS Institute, INC., Cary, NC). After the 12-week study period, youth in the wait-list control group will be invited to participate in the intervention. A subsample of youth (N=15) initially randomized to the intervention will be invited to participate in an exit in-depth interview.

4.1 Randomisation and Blinding

A computer-generated randomization list will be used to assign each subject to the intervention or wait-list control group in a 1:1 ratio. We recognize that differences may exist in PA practices and body weight, T2D morbidity, and intervention treatment effect by sex. However, no formal stratification will be conducted because this is a feasibility study with a limited sample size and the feasibility outcomes are primary. Instead, we will aim to recruit equal numbers of males and females. To minimize selection bias and ensure equal numbers of intervention or wait-list control, randomization will be blocked using random sequences of block sizes (4, 6, and 8). SAS version 9.4 (SAS Institute, INC., Cary, NC) will be used to perform the randomization. To ensure blinding of the study biostatistician, the randomization scheme will be implemented by a staff member at a collaborating community clinic who is not involved in recruitment or daily interactions with study subjects. This individual will be identified when the research team meets with clinic personnel to develop recruitment protocols for each clinic.

5 Statistical Analysis

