## Section G: Sample Size/Data Analysis

### G1. Sample Size

How many subjects (or specimens, or charts) will be used in this study?

Local: 98      Worldwide: 98

Please indicate why you chose the sample size proposed:

Qualitative interviews will be conducted among 30 adolescents, 20 parents will be invited to complete a parent survey, and 48 adolescents will be recruited for participation in the intervention component. A formal power calculation was not used as the primary purpose of this study is to examine feasibility, which is adequate for estimating feasibility parameters needed to inform a fully powered intervention.

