5.5 Exploratory Analyses of Secondary and Tertiary Outcomes (Aim 2)

Subgroup analyses by gender will be conducted as exploratory using summary statistics since the study is not power to detect an effect by gender.

A repeated measures model will be used to examine change in PA, SB and sleep. Each outcome will be tested in a separate model. The model will include time, treatment group, and the time by treatment group interaction. The magnitude and direction of the associations using parameter estimates and associated confidence intervals. Potential covariates include subject age, gender and BMI.

Compositional data analysis will be conducted for the PA, SB, and sleep behaviors. After log transformation, the geometric mean of each behaviour and all behaviors together (overall) will be calculated. The log-ratio of each behaviour will be derived by dividing the geometric mean of each behavior by the overall geometric mean. Differences by treatment group will be assessed using t-test. Variability of each behaviour in relation to the other behaviors and variance of the whole composition will be described using a variation matrix. The association of treatment group with the behaviors will be examined using multivariate regression (all outcomes as dependent variables in one model), after adjusting for gender.

References

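### Equal overall recruitment of boys and girls does not balance sex between the arms, and the main between-arm tests of the secondary and tertiary outcomes carry no term for sex

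*SAP*

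**What the plan says.** SAP 4.1 (Randomisation and Blinding) recognises that "differences may exist in PA practices and body weight, T2D morbidity, and intervention treatment effect by sex". It then states that "no formal stratification will be conducted because this is a feasibility study with a limited sample size and the feasibility outcomes are primary", and continues: "Instead, we will aim to recruit equal numbers of males and females". Allocation is 1:1 from one computer-generated list, in random blocks of 4, 6 and 8. The blocks balance arm size and are not kept separately by sex.

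SAP 5.4, the main analysis of the secondary and tertiary outcomes, compares continuous variables between arms by t-test or Mann-Whitney test. Protocol G2 names only the Mann-Whitney test between groups. Neither includes sex.

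Sex does appear in SAP 5.5, which is exploratory:
- Summary statistics are planned by gender.
- The compositional multivariate regression is adjusted for gender.
- For the repeated measures model, "Potential covariates include subject age, gender and BMI".

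On size, Protocol G1 says that "48 adolescents will be recruited for participation in the intervention component" and that "A formal power calculation was not used as the primary purpose of this study is to examine feasibility". Protocol F2, under the exit interviews, reports that data collection is complete with 43 participants in the database. Their split by arm and sex is not given.

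**The concern.** Stratification and an equal-numbers target do different things. Stratification controls the sex split between arms. The target controls only the total. Joining the two with a word that signals replacement invites the reader to think that sex has been dealt with in the arm comparison, and it has not.

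If the arms differ in sex mix by chance and boys and girls differ on the outcome, part of that difference is carried into the estimated intervention effect. Protocol G2 intends these analyses to guide power calculations for later trials, so the estimates themselves matter as well as the p-values. The one repeated measures model that could absorb the imbalance leaves the use of sex to the analyst.

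**Working it through.** The plan gives no figure for sex imbalance, sex effect, SD or power, so there is nothing of its own to reproduce.

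**Inputs.** From the documents: 48 randomised (Protocol G1), 1:1, no stratification, blocks of 4, 6 and 8 (SAP 4.1). Derived: 24 per arm, and 24 boys and 24 girls if the target is met. Assumed: boys and girls differ by d = 0.3, 0.5 or 0.8 within-sex SD on the analysed quantity.

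**Step 1: chance imbalance.** Let K be the number of boys in one arm. Then P(K = k) = C(24,k) × C(24,24−k) / C(48,24), and the arms differ by |2k − 24| boys.
- P(K = 12) = 0.2268; P(11) = P(13) = 0.1932; P(10) = P(14) = 0.1193.
- P(difference of 4 or more) = 1 − (0.2268 + 2 × 0.1932) = 0.387.
- P(difference of 6 or more) = 0.387 − 2 × 0.1193 = 0.148.

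Simulating the SAP's blocks (100,000 runs, arm sizes free to differ slightly), with the thresholds expressed as 4/24 = 16.7 and 6/24 = 25 percentage points in the proportion of boys, gives 34.7% and 13.1%.

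**Step 2: does equal recruitment help?** With 12 boys and 36 girls the exact probabilities are 31.8% and 9.3%. The SD of the between-arm difference in proportion of boys is 0.146 at 24:24 and 0.126 at 12:36. A 50:50 mix therefore does not reduce the expected imbalance; it raises it slightly.

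**Step 3: the database of 43.** Assuming splits of 21 and 22 by sex and by arm, the SD is 0.154 and P(25 points or more) = 13.1%. The picture is the same.

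**Step 4: effect on the estimate.** Shift = d × (difference in boys)/24. Unadjusted variance = 1 + d²/4 (sexes 50:50). Unadjusted SE = √[(1 + d²/4) × 2/24]; with no sex effect this is √(2/24) = 0.289.

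| d (assumed) | Shift, 4 boys | Shift, 6 boys | Unadjusted SE | Variance share of sex, (d²/4)/(1 + d²/4) |
|---|---|---|---|---|
| 0.3 | 0.05 | 0.08 | 0.292 | 2% |
| 0.5 | 0.08 | 0.13 | 0.298 | 6% |
| 0.8 | 0.13 | 0.20 | 0.311 | 14% |

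The largest shift is 0.20/0.311 = 0.64 of a standard error.

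**Step 5: what adjustment gains.** Estimating the sex term inflates the variance of the contrast by about 1/(1 − 1/47) = 1.022. The variance ratio, adjusted to unadjusted, is then 1.022/1.0225 = 1.00, 1.022/1.0625 = 0.96 and 1.022/1.16 = 0.88. The gain runs from nothing to about 12% of variance.

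**Step 6: level or change.** SAP 5.4 does not say whether the between-arm test uses post-intervention values or changes from baseline. For post-intervention values, d is the sex difference in level and the table applies directly. For changes, a stable sex difference cancels, and d is only the sex difference in change, which may be much smaller.

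**The case against.** The case for leaving the plan alone has real weight.

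- **Purpose of the target.** The SAP never says that equal recruitment balances the arms. Equal numbers make the smaller sex group as large as possible, which serves the gender summaries in SAP 5.5. That benefit stands. The wording still presents the target as what is done in place of stratification, and for the arm comparison it is not a replacement.
- **Validity.** A reader might infer that the main comparison is unprotected or biased. The documents do not support that. Randomisation is the protection, and chance imbalance in sex is part of the variation that the t-test's standard error already reflects. What remains is the estimate in this one small trial, and some precision.
- **Strength of the SAP's statement.** A reader might take the SAP to assert that sex affects these outcomes. It says only that differences may exist, and it gives no size.
- **Sex ignored altogether.** This would also be too strong: SAP 5.5 uses gender in three places. SAP 5.1 already summarises variables by treatment group, so sex by arm should be reported anyway.
- **Frequency.** A 35 to 39% chance of a 4-boy difference makes it common, not likely.
- **Stakes.** SAP 5.4 calls these analyses preliminary, and none of the six feasibility criteria in SAP 3.2 is a between-arm test.
- **Cost.** The Mann-Whitney test takes no covariate, so adjustment changes the main method. This is correct and belongs in the price of the fix.

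**Conclusion.** The point holds in a limited form. Equal overall recruitment does not substitute for stratification in the arm comparison, and the main between-arm tests do not account for a factor that the SAP itself names. Not stratifying is defensible in a feasibility trial of 48.

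The consequence is modest. A difference of 4 or more boys has probability 35 to 39%, and of 6 or more 13 to 15%. Imbalances of 4 to 6 boys would shift an estimate by about 0.05 to 0.20 SD, always below one standard error. These shifts rest on assumed sex differences of 0.3 to 0.8 SD in the analysed quantity, for which the documents give no figure, and they shrink if changes from baseline are analysed. This is a minor, worthwhile correction to estimates meant to inform later trials. It does not invalidate the planned tests or touch the primary feasibility conclusion.

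**What to change.** 1. Keep the unstratified scheme, and reword SAP 4.1 so that equal recruitment is described as supporting the gender summaries and not as replacing stratification.
2. In SAP 5.4, make a linear model with sex as a fixed covariate the main between-arm comparison for each continuous secondary and tertiary outcome. Keep the t-test or Mann-Whitney test as supportive, and bring Protocol G2 into line.
3. One route is to promote the SAP 5.5 repeated measures model and remove the optional status of sex. It then needs a sex-by-time term: with complete data at two time points, a sex main effect alone leaves the time-by-treatment estimate unchanged. A model of the post-intervention value on arm, baseline value and sex is the simpler alternative.
4. State whether the analysed quantity is the post-intervention value or the change, and report sex by arm at baseline.

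Cost: SAP and protocol wording, and one degree of freedom (two for the repeated measures version with its sex-by-time term). Sex is already collected. If sex is only weakly prognostic for the analysed quantity, there is little or no gain in precision. A main-effect covariate does not address a treatment effect that differs by sex; the exploratory gender summaries remain the place for that. Because data collection has ended, the change must be dated and declared as made after data collection.

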5.1 General Considerations

Analyses will be conducted on all subjects based on the treatment group assigned (intervention or wait-list control) according to the intent-to-treat principal. All statistical tests will be 2-sided and performed using a 5% significance level, leading to 95% (2-sided) confidence intervals. Variables will be summarized overall and by treatment group (intervention, wait-list control). Continuous variables will be described using number of subjects, mean, standard deviation, median, 25th percentile, 75th percentile, minimum, and maximum. Skewness, kurtosis, tests for location and histograms will be examined to assess normality and the need for variable transformations. Bivariate continuous variables will be depicted using scatterplots and the Spearman correlation coefficient. Categorical variables will be described using number of subjects and percentages. Denominators of percentage calculations will be based on the number of subjects in the treatment group (intervention or wait-list control).

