5.2 Missing Data

The pattern of missing data will be described for the secondary and tertiary outcomes. Differences in subject characteristics (demographics, BMI) and outcomes by whether or not the subject started the intervention or completed the study will be examined.

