5.4 Main Analyses of Secondary and Tertiary Outcomes (Aim 2)

Since this is a feasibility study, quantitative assessment of the outcomes will be considered preliminary. The objective of these preliminary analyses is to demonstrate whether the intervention shows promise in changing the PA, SB, and sleep behaviors. Emphasis will be placed on describing the variability in the outcomes using measures of central tendency including mean, standard deviation, and 95% confidence intervals.

Comparisons of continuous variables between treatment groups will be conducted using t-tests or a non-parametric analogue (Mann-Whitney U test). Comparisons within treatment group will be tested using paired t-tests or the signed rank test. Comparisons of categorical variables between groups will be assessed using Chi-square or Fisher's exact tests; McNemar test will be used within groups. The reliability of the psychological needs and autonomous motivation scales will be assessed using Cronbach's alpha. Examination of clinically meaningful effects,¹⁵ and estimation of the reliable change index¹⁶ will be conducted.

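### The SAP promises an intent-to-treat analysis of all subjects, but its main tests of the secondary and tertiary outcomes are complete-case tests with no method for missing 12-week data

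*SAP*

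**What the plan says.** SAP 5.1 sets the analysis population: "Analyses will be conducted on all subjects based on the treatment group assigned (intervention or wait-list control) according to the intent-to-treat principal".

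SAP 5.4, which holds the main analyses of the secondary and tertiary outcomes, names the tests. Between arms: "Comparisons of continuous variables between treatment groups will be conducted using t-tests or a non-parametric analogue (Mann-Whitney U test"). Within arms: "Comparisons within treatment group will be tested using paired t-tests or the signed rank test". Categorical outcomes get chi-square or Fisher tests between arms and McNemar within arms. The section does not say whether the between-arm test is of 12-week values or of change. It also limits the weight of these results: "Since this is a feasibility study, quantitative assessment of the outcomes will be considered preliminary".

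SAP 5.2 is the whole missing-data plan. Its first sentence is "The pattern of missing data will be described for the secondary and tertiary outcomes". Its second compares subject characteristics and "outcomes by whether or not the subject started the intervention or completed the study will be examined". Neither the SAP nor protocol G2 states an imputation method, a missing-data assumption or a sensitivity analysis.

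SAP 5.5, headed exploratory, adds: "A repeated measures model will be used to examine change in PA, SB and sleep". The terms are time, group and their interaction. The method of fitting and the treatment of incomplete records are not given.

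**The concern.** Intent-to-treat has two parts: subjects are analysed as assigned, and all of them are analysed. The first is kept. The second is not delivered by the 5.4 tests, because a t-test, Mann-Whitney, paired, signed rank or McNemar test drops a youth without the 12-week value. Tests of change and paired tests also drop a youth without a valid baseline.

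The plan expects such gaps. The data-collection criterion in SAP 3.2 accepts 85% at post-intervention. The accelerometer rule in protocol F2 (at least 18 hours on at least 4 days, one of them a weekend day) means that a youth can attend and still have no usable activity or sleep outcome.

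At stake is the between-arm contrast. SAP 5.4 uses it to judge whether the intervention shows promise, and protocol G2 says that these analyses will guide power calculations. If loss depends on baseline behaviour and differs by arm, the contrast partly reflects who stayed. A larger sample would not remove that bias, and the confidence interval does not show it.

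**Working it through.** The plan gives no power, effect-size or SD figure to reproduce; protocol G1 says that no formal power calculation was used.

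**Inputs from the documents.** 48 youths randomised 1:1, so 24 per arm; 85% with post-intervention data (SAP 3.2); two-sided 5% tests (SAP 5.1).

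**Assumed inputs.** Pre-post correlation, loss by arm, the dependence of loss on baseline, and the rate of valid accelerometry. The documents give none of these.

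**1. Number analysed.** 0.85 × 48 = 40.8, so 41 youths meet the criterion and 7 may be missing. The 95% half-width for a between-arm difference, 1.96 × √(2/n) in SD units, is 0.57 at n = 24 per arm and 0.61 at n = 20.5.

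**2. Accelerometry.** Let v be the chance of a valid record per visit, assumed independent across visits.
- Change and paired tests use 48 × 0.85 × v² youths.
- A model that accepts one valid visit uses 48 × [1 − (1 − v)(1 − 0.85v)] youths.

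| v (assumed) | both visits valid | at least one valid |
|---|---|---|
| 0.7 | 20.0 | 42.2 |
| 0.8 | 26.1 | 44.9 |
| 0.9 | 33.0 | 46.9 |

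This applies only to accelerometer outcomes. The model does not recover missing 12-week values; it keeps the information in the baseline record.

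**3. Bias by simple arithmetic.** If completers exceed dropouts by g SD in both arms, the bias in final values is g × (m_I − m_C)/24, where m_I and m_C are the numbers missing in the intervention and control arms. Take 7 losses and g from 0.25 to 1.0:
- split 4 and 3: 0.25 × 1/24 = 0.01 to 1.0 × 1/24 = 0.04 SD
- all 7 in one arm: 0.25 × 7/24 = 0.07 to 1.0 × 7/24 = 0.29 SD

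**4. Bias by simulation.** No true effect, 24 per arm, correlation 0.6, loss driven by observed baseline. In the adverse case, the intervention log-odds of loss are ln(0.15/0.85) − 1.5 × baseline (in SD), and control loss is a flat 5%.

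| Loss pattern (assumed) | Final values | Change |
|---|---|---|
| Intervention slope −1.5, loss 22% vs 5% | +0.15 SD | −0.10 SD |
| Intervention slope −0.5, loss 21% vs 5% | +0.06 SD | −0.04 SD |
| Slope −1.5 in both arms, loss about 18% each | 0.00 | 0.00 |

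In the adverse case the likelihood time-by-arm contrast from all available data has bias 0.00 SD. The sampling SD of one trial's completer estimate is 0.31 (final) and 0.28 (change). Average retention is 86%, but only about 67% of simulated trials reach the 41 youths that the criterion needs. With correlation 0.5 to 0.7 and somewhat heavier loss in one arm, the biases are +0.12 to +0.17 SD (final) and −0.12 to −0.07 SD (change).

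The sign of the bias turns on whether final or change values are tested, which SAP 5.4 leaves open.

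**The case against.** The strongest reply is that these are not the trial's main results. SAP 3.2 makes feasibility primary and counts retention among its criteria, so loss will be reported as a finding in itself. SAP 5.4 calls the comparisons preliminary, and protocol G2 expects no clinically significant change. That stands. A reader might infer that the headline result is a biased completer analysis; the documents do not support this.

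Much of the diagnosis is already planned. SAP 5.1 reports the number of subjects by group, SAP 5.2 compares starters and completers, protocol G2 records dropouts and their reasons, and SAP 5.5 contains a suitable model. This softens the gap but does not close it. The model is exploratory, covers only activity, sedentary behaviour and sleep, and could be fitted in a way that deletes incomplete records.

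The adverse simulation is one chosen scenario. A reader might infer that loss did differ by arm because only the intervention arm carries weekly goals and texts. No loss by arm is reported. Controls also receive a Fitbit and are offered the intervention after 12 weeks, which gives them a reason to stay. Nor can the 43 participants in the database (protocol F2) be read as a retention count, because the protocol does not say whether they were enrolled, randomised or completed.

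Finally, data collection is over, so a change of main analysis could look data-driven. That is a reason to date and disclose it. It is not a reason to leave the 5.4 tests unlabelled.

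**Conclusion.** The inconsistency is established from the text: SAP 5.1 claims all subjects, SAP 5.4 cannot deliver that when 12-week data are missing, and SAP 5.2 supplies no method. Analysis by assigned arm is kept, and the primary outcome is unaffected.

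Bias in the preliminary contrasts is possible, not shown. Under baseline-driven loss with the assumed inputs it runs from 0 to about +0.15 SD on final values or −0.10 SD on change, about half or less of the sampling SD of roughly 0.3. The likelihood estimate removes it only if loss depends on observed data alone. Severity is low to moderate: it would seldom decide how this pilot is read, but it could carry into the design of a later trial.

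**What to change.** - **Main between-arm estimate.** Move the SAP 5.5 model (time, arm, time-by-arm) to 5.4 for activity, sedentary behaviour and sleep. Fit it by REML with unstructured covariance to every randomised youth with at least one valid visit, and state the missing-at-random assumption.
- **Tertiary outcomes.** Use the same model for the continuous ones: the BMI measure and the needs and motivation scores. Otherwise they stay on the complete-case tests.
- **5.4 tests.** Label them complete-case and supportive, say whether they use final or change values, and give the number contributing per arm and visit.
- **Optional.** Add a simple delta-shift analysis of missing 12-week values to probe missing-at-random.
- **Disclosure.** Data collection has concluded, so date the change and report it as made after that point.

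The cost is SAP wording and a little more analysis, since the model is new only for the tertiary outcomes. The downside is reliance on missing-at-random, which the data cannot verify.
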